9.5. Data collection: visits

This study is a retrospective study with no formal visit plan. Data post-procedure will be collected from the medical record database and health examination in Hainan medical pilot zone. All available follow up data before the end of study is suggested to be collected. The pages of follow up visits in CRF will be filled according the time.

Data below will be collected and recorded in CRF, if available:

Prostate volume(MRI, DUS), PVR, Uroflowmetry(Qmax, Urinary volume), IPSS score and QoL, sexual function (IIEF and MSHQ-EjD), surgical retreatment and medication for BPH/LUTS, adverse events.

Note: the enrolled subjects must be treated with Rezūm system in hospitals in Hainan Boao Medical Pilot zone, the follow-up visits could be performed in local hospital. the data can be collected and recorded in CRF, if available.

9.6. *Study Completion*

This study is a retrospective real world study with no formal visit plan, no visit must be performed. The end of study will be scheduled at 4 months post Rezūm procedure of last subject enrolled.

9.7. *Source Documents*

It is preferable that original source documents are maintained, when available. In lieu of original source documents, certified copies are required to be maintained. A certified copy is a copy (irrespective of the type of media used) of the original record that has been verified (i.e., by a dated signature or by generation through a validated process) to have the same information, including data that describe the context, content, and structure, as the original.

10. Statistical Considerations

10.1. *Primary Endpoints*

Primary Efficacy Endpoint: IPSS change at 3-6M post Rezūm procedure.

Primary Safety Endpoint: Device Related Serious Complications from Rezūm procedure to 3-6M post Rezūm procedure.

Composite device related serious complications for this endpoint are defined as:

1. Device perforation of the rectum or GI tract;
2. Device related formation of fistula between the rectum and urethra;
3. De novo severe urinary retention lasting more than 21 consecutive days post treatment.

10.1.1. *Hypothesis*

The primary endpoint is IPSS change at 3-6M post Rezūm procedure.

In Rezūm Pivotal II study, IPSS score represents a 11.2 ± 7.6 point reduction at 3M post Rezūm procedure in treatment arm, while 4.3 ± 6.9 point reduction in sham control. In Pivotal trial, IPSS score in treatment group decreased 25% (5.375) compared to sham control group is recognized as meaningful.

As this is a retrospective RWS study, the inclusion/exclusion criteria is not strict, we set up performance goal for score change as 5.5, the expected score change is 10 at 3-6M post Rezūm procedure. A performance goal (PG) testing for the primary endpoint is planned. The decision rule is to calculate the Lower Confidence Interval (LCI) of score change and compare it to the PG, meet PG if LCI is greater than PG.

10.1.2. *Sample size*

The sample size is calculated according to below formula:

$$n = \frac{(Z_\alpha + Z_\beta)^2 \sigma^2}{\delta^2}$$

n is sample size, we designed 5.5 as performance value, 10 is expected IPSS change, $\alpha=0.05$, $\beta=0.20$ (power=80%) Considering the small sample size needs to be iterative distribution, 22 subjects will provide more than 85% power. As this is retrospective study, there are chances of missing data in the study. So the final sample size will be up to 30, to satisfy 22 treated subjects.

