6.2.1.2. Primary Safety Endpoint

Primary safety endpoint: Device Related Serious Complications from Rezūm procedure to 3-6M post Rezūm procedure.

Composite device related serious complications for this endpoint are defined as:

1. Device perforation of the rectum or GI tract;
2. Device related formation of fistula between the rectum and urethra;
3. De novo severe urinary retention lasting more than 21 consecutive days post treatment.

AEs will be collected and relationship to device will be assessed by investigators, it will be assessed whether meet the pre-specific device related serious complications. It's uncertain that when subject's data of the last follow up get in this retrospective study, so serious complications in up to 6 months post procedure will be used for primary safety endpoint.

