### 3.1.3 Statistical Methods

Descriptive statistics will be used to summarize the study endpoints. Continuous variables will be tabulated with mean, median, standard deviation, minimum, maximum, and the corresponding 95% confidence interval of the mean. Categorical variables will be tabulated with frequencies, percentages along with the 95% confidence intervals.

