### 3.2 Primary Safety Endpoint

Primary Safety Endpoint: Device Related Serious Complications at 3-6M post Rezūm procedure.

Composite device related serious complications for this endpoint are defined as:

1. Device perforation of the rectum or GI tract
2. Device related formation of fistula between the rectum and urethra
3. De novo severe urinary retention lasting more than 21 consecutive days post treatment.

AEs will be collected and relationship to device will be assessed by investigators, it will be assessed whether meet the pre-specific device related serious complications. All serious complications in up to 6 months (i.e. 182 days) post procedure will be used for primary safety endpoint.

Frequencies and percentages will be provided for AE summary.

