#### **4.1.2 Safety Analysis Set**

The safety analysis set includes all enrolled subjects who has been treated with Rezūm system in hospitals in Hainan BOAO medical pilot zone.

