## **5.8 Other Analyses**

Missing data will be excluded for primary analysis in this small sample size study. Based on the missing data during data review, Imputation with mean or median where applicable for continuous variable, and tipping point analysis for categorical variable might be conducted for sensitivity analysis. Incorrect and unreasonable data will be clarified before database lock.

Subject disposition (e.g., number completing the study) will be summarized with frequency tables and percentages.

Non-serious AE's and SAE's will be summarized as the number of events and rate per subject by MedDRA system organ class (SOC) and preferred term.

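### The data cut-off can fall about 60 days before the end of the 182-day primary safety window, and the SAP does not show who was observed that long

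*Protocol*

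**What the plan says.** Protocol 9.6 fixes the close of the study: "The end of study will be scheduled at 4 months post Rezūm procedure of last subject enrolled". The note to Table 9.1-1 limits collection to information available before that end, and Protocol 9.5 and 9.6 require no visit. Under Protocol 9.3 a subject is enrolled when he consents, which is after treatment.

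The primary safety endpoint is titled as running from the procedure to 3-6 months. Protocol 6.2.1.2 admits that follow-up will vary, "It's uncertain that when subject's data of the last follow up get in this retrospective study", and draws the consequence: "so serious complications in up to 6 months post procedure will be used for primary safety endpoint". SAP 3.2 puts the limit in days: "All serious complications in up to 6 months (i.e. 182 days) post procedure will be used for primary safety endpoint".

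The planned analysis is brief. SAP 3.2 says "Frequencies and percentages will be provided for AE summary". SAP 3.1.3 adds intervals: "Categorical variables will be tabulated with frequencies, percentages along with the 95% confidence intervals". The denominator is in SAP 4.1.2: "The safety analysis set includes all enrolled subjects who has been treated with Rezūm system in hospitals in Hainan BOAO medical pilot zone". No minimum follow-up is set. SAP 5.8 plans a disposition table with study completion as its example, and says that "tipping point analysis for categorical variable might be conducted for sensitivity analysis". SAP 7.3 excludes missing data from the primary analysis. Its planned imputations for missing values are for continuous variables.

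**The concern.** A subject whose records must stop at about day 120 cannot contribute an event between then and day 182, yet he counts in full in the denominator of a proportion that reads as a 6-month result. If he is event-free when his records end, the truncation can only lower the 182-day proportion or leave it unchanged.

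The SAP also does not say whether such a subject is missing under SAP 7.3 or a non-event under SAP 4.1.2, so two programmers could report different denominators for a primary endpoint. The disposition table does not settle this, because completing the study is not defined as being observed to day 182.

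With at most 30 subjects, a count of zero or one is plausible, and its meaning depends on how much of the window was observed. Protocol 6.1 says that the data are meant to support approval in China, so readers will want that information.

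**Working it through.** The documents give no target rate, performance goal or sample size for the safety endpoint, so there is no safety figure to reproduce. The plan's only power figure is for efficacy (more than 85% with 22 subjects). It reproduces at 85.1% with a one-sided one-sample t-test and does not bear on the safety proportion.

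**Inputs.** Cut-off 4 months after the last enrolled subject's procedure (Protocol 9.6); safety window 182 days (SAP 3.2); IPSS window days 90 to 182 (SAP 3.1); up to 30 subjects (SAP 3.1.2). Assumptions, because the documents give no procedure dates or event timing: even treatment over A months, the last enrolled subject is also the last treated, records run to the cut-off, and the hazard is constant.

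**Shortfall for the last enrolled subject.** Four calendar months is 120 to 123 days. 182 − 123 = 59 days; 182 − 120 = 62 days. Someone treated more than about 60 days earlier loses nothing to the cut-off.

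**Share truncated and person-time lost, taking 60 days.** Share = 60 / (30.4 × A). The mean loss among those truncated is 30 days, so person-time lost = share × 30/182. Equivalents of full follow-up = 30 × (1 − loss). The zero-event two-sided 95% upper limit is 1 − exp(−3.689 / equivalents), where 3.689 = −ln(0.025).

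| Treatment period | Share truncated | Of 30 | Person-time lost | Equivalents | Upper limit, 0 events |
|---|---|---|---|---|---|
| Full follow-up | 0 | 0 | 0 | 30 | 11.6% |
| 12 months | 0.164 | about 5 | 2.7% | 29.19 | 11.9% |
| 6 months | 0.329 | about 10 | 5.4% | 28.37 | 12.2% |
| 3 months | 0.658 | about 20 | 10.8% | 26.75 | 12.9% |

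The full follow-up value equals the Clopper-Pearson limit for 0/30.

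**All 30 treated on one day.** 30 × 120/182 = 19.8 or 30 × 123/182 = 20.3 equivalents, giving limits of 17.0% or 16.6%. This is an illustration and not a bound: enrolment follows consent, so a subject may have been treated after the last enrolled subject and lose more than 62 days, and records may end before the cut-off.

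**Without the constant hazard, counting only subjects observed to day 182.** With no events the two-sided 95% Clopper-Pearson limit is 1 − 0.025^(1/n): 16.8% for n = 20, 21.8% for n = 15 and 30.8% for n = 10. These values discard partial follow-up and so are cautious.

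**Efficacy.** The last enrolled subject has 120 − 90 = 30 to 123 − 90 = 33 of the 182 − 90 = 92 days in the IPSS window. Because the last score in that window is used, the cut-off can affect whether a score exists and which one counts. Anyone treated more than about 30 days after the last enrolled subject's procedure cannot reach day 90 and falls outside the efficacy set.

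**The case against.** The strongest reply is that the plan is coherent as written. A 4-month close lies inside the titled range of 3-6 months. The 6-month wording can be read as a cap on which events count and not as a promise to observe everyone for 182 days, and Protocol 6.2.1.2 gives uncertain follow-up as its reason. This stands against a reader who might infer that the protocol flatly contradicts itself; the documents do not support that. It does not answer the analysis gap, because a cap on events sets no rule for the denominator and does not report exposure.

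A second reply is that the data are retrospective, so every subject may already be past 6 months, and that these complications tend to come early. Protocol 4.1 reports no late adverse events in the pivotal study, although it does not define late. Both could make the effect negligible, and a constant hazard may overstate it. Neither can be confirmed from the documents, and the stated cut-off permits shorter follow-up.

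A third reply is that this is preliminary safety in up to 30 subjects with no safety hypothesis. That stands, and it limits the weight of the point.

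**Conclusion.** The concern holds as a mismatch between cut-off and window, combined with an analysis that does not show how much of the window was observed. The weight is minor to moderate. Under even treatment over 3 to 12 months and a constant hazard, the zero-event limit rises by 0.3 to 1.3 percentage points (11.6% to between 11.9% and 12.9%). The actual size is unknown without procedure dates.

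Two stronger readings go too far. A reader might infer that the reported safety percentage must be too low. Truncation alone can act only in that direction, but SAP 7.3 dates an event with no onset date to the procedure, which can bring an event from after day 182 into the window, so the reported figure as a whole has no fixed direction. A reader might also infer that the efficacy test is undermined. The documents do not support that either: a score from day 90 onward qualifies, and a subject followed for 4 months can supply one. It would be equally wrong to call efficacy untouched, given the shortened IPSS window.

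**What to change.** 1. **Protocol 9.6.** Set the data cut-off at 182 days after the latest procedure among enrolled subjects. Chart extraction then closes about 2 months later, or more if the latest-treated subject was treated after the last enrolled one. No visit is added and enrolment is not restricted.

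2. **SAP 3.2, needed in either case, because no visit is mandated and a later cut-off does not by itself secure follow-up.** Add text such as:

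> Days from procedure to last documented contact will be summarised (median, minimum, maximum), with the number of subjects observed to day 182. The crude proportion of the safety analysis set with a composite event will be reported with a two-sided 95% Clopper-Pearson interval; event-free subjects whose contact ends before day 182 remain in this denominator. As a sensitivity analysis, the Kaplan-Meier estimate at day 182 will be given with its 95% interval, censoring event-free subjects at the earlier of last documented contact and day 182. If there are no events, the two-sided 95% Clopper-Pearson upper limit among subjects observed to day 182 will be given instead. Censoring at last contact may be informative, because contact may depend on symptoms.

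In the zero-event case, 0/20 would give 16.8%, on the same scale as the crude proportion. The SAP change costs one short paragraph and one small table. If a later cut-off is not feasible, it still makes the safety result interpretable.

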10.2. General Statistical Methods

10.2.1. Analysis Sets

This real world study plans to collect medial data of BPH patients who has been treated with Rezūm system in Hainan BOAO medical pilot zone.

The efficacy analysis set includes subjects with IPSS scores at baseline and at 3-6 months post-procedure.

The safety analysis set includes all subjects who has been treated with Rezūm system in hospitals in Hainan BOAO medical pilot zone.

10.2.2. Control of Systematic Error/Bias

All subjects treated with treated with Rezūm system in Hainan BOAO medical pilot zone will be enrolled to reduce select bias during given time. The data will be collected completely and accurately, stratified analysis or Multivariate analysis may be used to find and control the bias.

10.2.3. The method of handling missing, incorrect data(including subjects withdrawal and lost to follow-up) and unreasonable data

Missing data will be excluded for primary analysis in this small sample size study. Imputation with mean or median where applicable for continuous variable, and tipping point analysis for categorical variable might be conducted for sensitivity analysis. Incorrect and unreasonable data will be clarified before database lock.

10.2.4. Data Analyses

Study endpoints will be summarized descriptively, when it comes to primary endpoint-IPSS score, last IPSS score during 3-6 month post procedure of subjects will be used, if they had several IPSS questionnaires. Continuous variables will be tabulated with mean, median, standard deviation, minimum, maximum, and 95% confidence interval of the mean. Categorical variables will be tabulated with frequencies, percentages and 95% confidence intervals.

This study may allow explorative statistics based on collected data, which may include, but is not limited to, the change tendency of IPSS score and variables, sub-group analysis based on IPSS score. All the analysis details will be added in statistical analysis plan.

11. Data Management

11.1. *Data Collection, Processing, and Review*

Subject data will be recorded in a limited access secure electronic data capture (EDC) system.

The clinical database will reside on a production server hosted by Medidata EDC System. All changes made to the clinical data will be captured in an electronic audit trail and available for review by the sponsor or its representative. The associated Rave software and database have been designed to meet regulatory compliance for deployment as part of a validated system compliant with laws and regulations applicable to the conduct of clinical studies pertaining to the use of electronic records and signatures. Database backups are performed regularly.

The Investigator provides his/her electronic signature on the appropriate electronic case report forms (eCRFs) in compliance with local regulations. A written signature on printouts of the eCRFs must also be provided if required by local regulation. Changes to data previously submitted to the sponsor require a new electronic signature by the Investigator acknowledging and approving the changes.

Visual and/or electronic data review will be performed to identify possible data discrepancies. Manual and/or automatic queries will be created in the Medidata EDC system and will be issued to the site for appropriate response. Site staff will be responsible for resolving all queries in the database.

All access to the clinical database will be changed to “Read only” after all data is either “Hard Locked” or “Entry Locked”. Once acceptance of the final report or finalization of publications (as applicable) is received, final database storage and archiving activities can begin. Once all of the closeout activities are completed a request to IT is submitted to have the “Database Locked” or Decommissioned and all database access revoked.

11.2. *Data Retention*

The Principal Investigator or his/her designee or Investigational site will maintain all essential study documents and source documentation that support the data collected on the study subjects in compliance with applicable regulatory requirements. Documents must be retained for 10 years after the formal discontinuation of the clinical investigation of the product. These documents will be retained by BSC until the product/device is no longer in use in compliance with local regulations.

The Principal Investigator or his/her designee will take measures to prevent accidental or premature destruction of these documents. If for any reason the Principal Investigator or his/her designee withdraws responsibility for maintaining these essential documents, custody must be transferred to an individual who will assume responsibility and BSC must receive written notification of this custodial change. Sites are required to inform Boston Scientific in writing where paper or electronic files are maintained in case files are stored off site and are not readily available.

12. Amendment

The investigator should adhere to the approved protocol. Any modification to the protocol (management information or alterations of the study, etc.) during the study implementation shall be submitted to the EC for approval or recorded by the investigator upon approved by the sponsor. Appropriate approvals (e.g., EC) of the revised protocol must be obtained prior to implementation.

13. Compliance

13.1. *Statement of Compliance*

This real world study is financed by the study sponsor. Before the investigational site can be “Authorized to Enroll,” the investigational site must enter into a Clinical Study Agreement with the sponsor that details the financing of the study as well as the rights and obligations of the investigational site and the investigator. This study will be conducted in accordance with ISO14155, ICH-GCP, ethical principles that have their origins in the Declaration of Helsinki, and applicable Chinese laws and regulations. The study shall not begin until the required approval/favorable opinion from the IRB/EC and/or regulatory authority has been obtained, if appropriate. Also, the study shall not begin prior to issuance of the site Authorization to Enroll, as provided by the sponsor. Any additional requirements imposed by the IRB/EC or regulatory authority shall be followed, if appropriate.

13.2. *Investigator Responsibilities*

The Principal Investigator of an investigational site is responsible for ensuring that the study is conducted in accordance with the Clinical Study Agreement, the clinical investigation plan, the spirit of ISO 14155, ethical principles that have their origins in the Declaration of Helsinki, any conditions of approval imposed by the reviewing IRB/EC, and prevailing local and/or country laws and/or regulations, whichever affords the greater protection to the subject.

The Principal Investigator's responsibilities include, but are not limited to, the following.

- Prior to beginning the study, sign the Clinical Study Agreement and comply with the Investigator responsibilities as described in such Agreement.
- Prior to beginning the study, sign the IB (if available) and protocol, and comply with study schedule in protocol.
- Provide his/her qualifications and experience to assume responsibility for the proper conduct of the study and that of key members of the site team through up-to-date curriculum vitae or other relevant documentation and disclose potential conflicts of interest, including financial, that may interfere with the conduct of the clinical study or interpretation of results.
- Create and maintain source documents throughout the clinical study and ensure their availability with direct access during monitoring visits or audits; ensure that all clinical-investigation-related records are retained per requirements.

- Ensure the accuracy, completeness, legibility, and timeliness of the data reported to the sponsor in the CRFs and in all required reports.
- Record, report, and assess (seriousness and relationship to the device/procedure) every adverse event as applicable per the protocol and observed device deficiency.
- Report to sponsor, per the protocol requirements, all reportable events.
- Report to the IRB/EC and regulatory authorities any SAEs and device deficiencies that could have led to a SADE and potential/USADE or UADE, if required by applicable laws or regulations or this protocol or by the IRB/EC, and supply BSC with any additional requested information related to the safety reporting of a particular event.
- Allow the sponsor to perform monitoring and auditing activities, and be accessible to the clinical research monitor or auditor and respond to questions during monitoring visits or audit(s).
- Allow and support regulatory authorities and the IRB/EC when performing auditing activities.
- Ensure that an adequate investigation site team and facilities exist and are maintained and documented during the clinical investigation.

All investigators will provide their qualifications and experience to assume responsibility for their delegated tasks through up-to-date curriculum vitae or other relevant documentation and disclose potential conflicts of interest, including financial, that may interfere with the conduct of the clinical study or interpretation of results.

Delegation of Responsibility

When specific tasks are delegated by an investigator, including but not limited to conducting data collection process, the Principal Investigator is responsible for providing appropriate training, are competent to perform the tasks they have been delegated and adequate supervision of those to whom tasks are delegated. Where there is a sub investigator at a site, the sub investigator should not be delegated the primary supervisory responsibility for the site. The investigator is accountable for regulatory violations resulting from failure to adequately supervise the conduct of the clinical study.

